1.1. Background and rationale

1.1.1. Background

The severe acute respiratory syndrome coronavirus 2 (SARS-CoV-2) emerged in late 2019. By mid-July 2020 14 million people globally had been infected, of which over 600,000 died of coronavirus disease 2019 (COVID-19) (1). In the UK, nearly 20% of patients hospitalised with COVID-19 were transferred to an intensive care unit (ICU) or high dependency ward (2). In total, over 10,000 patients have been treated for COVID-19 on an ICU in England and Wales. On average, 50% of these patients survived to hospital discharge, although survival rates appeared to increase over this period (3,4). The long-term impact on the health of survivors is unknown.

Previous studies have shown that critically ill patients who survive ICU treatment are at greater risk of death and report lower health-related quality of life when compared with population norms (5–7). While pre-existing comorbidities partially account for these differences, organ damage caused by critical illness and the impact of intensive organ support given in the ICU likely also play a role (8). Analysis by the Intensive Care National Audit and Research Centre (ICNARC) suggests that patients admitted with COVID-19 receive higher intensity organ support and suffer more complications than observed in other viral respiratory infections (4). For example, nearly all COVID-19 patients required respiratory support, with nearly 60% receiving mechanical ventilation (compared to 43% with viral pneumonias) (4). Around one third of patients also required advanced cardiovascular or renal support (4,9). Cardiac (myocarditis, heart failure, arrhythmias, acute coronary syndrome) and venous thrombotic complications (e.g. pulmonary embolism) were not uncommon (10–12). Although rare, some patients developed neurological complications such as stroke, encephalitis and Guillain-Barré syndrome (13).

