4.4. Cohort definitions

4.4.1. Patients with confirmed COVID-19 between 1st January to 1st July 2020 This group will consist of all individuals who were admitted to an intensive care unit between 1st January and 1st July 2020 with a confirmed diagnosis of COVID-19.

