5.1. Baseline patient characteristics

We will describe the characteristics of patients at the time of ICU admission, including demographics and clinical characteristics (listed in Section 5.2). These will be presented for each cohort separately. Data will be presented as mean with standard deviation (SD) when normality distributed or median and interquartile range for skewed variables. Categorical variables will be presented as number and proportion.

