5.2. Assumed confounding covariates

The following variables are assumed to be related to the risk of experiencing one or more of the outcomes, and will therefore be included in the baseline characteristics table, be included as covariates in the multivariable regression models, and be included as covariates in the propensity scores.

- Patient demographics: age, sex, ethnicity, index of multiple deprivation (IMD), body mass index (BMI), clinical frailty score, smoking status, month of admission, dependency prior to ICU admission (fully/partial/total assistance with activities of daily living), geographical region
- Medical history: comorbidities (as per Elixhauser (14)), dialysis-dependent, total length of previous hospital admissions in year prior to ICU admission.
- Hospital/ICU stay characteristics: Length of hospital stay prior to ICU transfer, Length of ICU stay, length of hospital stay after discharge from ICU, hospital region, month of admission.
- Acuity: APACHE-II/ICNARC severity score at admission, length of mechanical ventilation, length of advanced organ support (cardiovascular, respiratory, renal, liver, neurological)

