5.4.3. Comparison of COVID-19 cohort to other cohorts using propensity score matching

For each comparison of the COVID-19 cohort to a non-COVID cohort we will use propensity score matching to create cohorts that are similar in terms of baseline characteristics and confounding variables. We will construct a propensity score using logistic regression where the outcome is the cohort status, and the covariates will be those previously defined in Section 5.2. The model will allow for non-linear relationships between continuous variables and the outcome. The propensity score will then be estimated for each patient. One to one matching will be performed based on the

propensity score, initially using a nearest neighbour (greedy) approach. We will assess the balance achieved through the matching process using standard approaches, such as Q-Q plots, and assessments of the absolute standardised mean difference. If the covariates are not well balanced after nearest neighbour matching, alternative approaches will be tested, such as full matching, until sufficient balance is achieved. If sufficient balance cannot be achieved or too many patients from the COVID cohort are removed by the matching algorithm, we will consider using the propensity score for inverse probability weighting in our Cox regression models.

Once matched cohorts have been identified, we will analyse the outcomes with the standard regression modelling as described in Section 5.4.2– using Cox regression for the death outcome, and competing risk approaches for the secondary outcomes. However, since the data will now be clustered due to the matching, we will need to account for this in the regression models. We will therefore use cluster-robust standard errors.

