5.8. Statistical software

It is expected that all analysis will be carried out using R statistical software.

6. Conclusion

The intention of this study is to understand the long-term consequences of being admitted to ICU with COVID-19. Initially analyses will be descriptive in nature. We will then go on to summarise whether these long-term consequences are different from those that are associated with admission to ICU for other causes. We will use different comparison cohorts and different analysis methods to check the robustness of our conclusions.

This statistical analysis plan presents the principles of the analysis that we intend to follow in the OPTIC-19 study. We hope that by pre-specifying our analyses we will minimise the risk of reporting bias and data driven results.

7. References

- 1. World Health Organization. Coronavirus disease (COVID-19) Situation Report 183. 2020.
- 4. Intensive Care National Audit and Research Centre (ICNARC). ICNARC report on COVID-19 in critical care (17th July 2020). 2020;
- 6. Bion J. Long-term survival after intensive care. BMJ [Internet]. 1990 Dec 8;301(6764):1336– 1336. Available from: http://www.bmj.com/cgi/doi/10.1136/bmj.301.6764.1336

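### Every adjusted analysis specified in the SAP holds ICU course equal without saying so; an admission-only analysis on a hospital-discharge clock should sit beside it

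*SAP*

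**What the plan says.** SAP 5.2 gives one list of assumed confounders, chosen because they are thought to be related to the outcomes. Beside demographics, history and admission severity it contains "Length of ICU stay, length of hospital stay after discharge from ICU" and "length of mechanical ventilation, length of advanced organ support". SAP 5.1 presents the same list as "characteristics of patients at the time of ICU admission, including demographics and clinical characteristics (listed in Section 5.2").

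The list feeds every adjusted analysis that SAP section 5 specifies:

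- Propensity score (5.4.3): "the covariates will be those previously defined in Section 5.2".
- Fallback if matching fails (5.4.3): "we will consider using the propensity score for inverse probability weighting in our Cox regression models", which is the same score.
- Multivariable sensitivity models (5.6): the 5.2 variables again.

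The regression in 5.4.2 is reported unadjusted, and the subgroups in 5.5 are unadjusted or matched.

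The exposed cohort (SAP 4.4.1) is everyone "admitted to an intensive care unit between 1st January and 1st July 2020 with a confirmed diagnosis of COVID-19". Outcomes are timed from ICU discharge (Protocol 6 and 11.2; SAP 1.2 and 2.4), and SAP 4.1.2 excludes patients who died in hospital after ICU treatment. Other places describe follow-up from hospital discharge (Protocol 2, 5 and 7.1; SAP 1.1.2 and 2.1).

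**The concern.** Exposure is fixed at ICU admission. Lengths of ICU stay, ventilation, organ support and later ward stay are unknown then and may themselves depend on having COVID-19. SAP 1.1.1 says COVID-19 patients receive more intensive organ support and that, for later harm, "the impact of intensive organ support given in the ICU likely also play a role". Matching on these lengths removes whatever part of the COVID-19 difference runs through them. SAP section 6, however, says the study is to "understand the long-term consequences of being admitted to ICU with COVID-19". A reader could take the matched hazard ratio as the answer to that, when it answers a narrower question. The multivariable check cannot reveal the gap because it uses the same variables.

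The second issue is the clock. With the origin at ICU discharge and in-hospital deaths removed, nobody in the cohort can die between ICU discharge and hospital discharge. If that stretch differs in length between groups, comparisons not balanced on it are distorted.

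**Working it through.** **Plan's own figure.** 90,000 × 3.5 + 4,600 = 319,600, as stated in SAP 2.2. (90% of 5,000 is 4,500 rather than 4,600; nothing here depends on that.)

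**1. Which adjusted analyses use admission variables only?** Matching, weighting and the multivariable models all use the full 5.2 list, so within SAP section 5 the answer is none. The exploratory comparison of pregnant patients with an age-matched control group (Protocol 6, SAP 1.2) would be an exception, but section 5 gives no method for it.

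**2. How far apart could the two targets be?** Illustration with ventilation as yes/no (the SAP uses length). SAP 1.1.1 gives 60% ventilated with COVID-19 and 43% with viral pneumonia, for admissions rather than survivors. Let h be an assumed hazard ratio for ventilation, and let the COVID-19 ratio at equal ventilation be 1. The ratio without adjustment for ventilation is then approximately (1 + 0.60(h − 1)) / (1 + 0.43(h − 1)).

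| h | 0.7 | 0.8 | 1.5 | 2 | 3 |
|---|---|---|---|---|---|
| ratio | 0.94 | 0.96 | 1.07 | 1.12 | 1.18 |

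For scale, take 4,600 matched pairs and assumed one-year mortality of 5%, 10% or 20%. Deaths are D = 9,200 × mortality = 460, 920 or 1,840. With SE = 2/√D, the 95% limits around a ratio of 1 reach exp(1.96 × SE) = 1.20, 1.14 or 1.10. The gap between targets could be of that order, or nil.

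**3. Death-free ward time.** Assumptions: true ratio 1 after hospital discharge, flat hazard, 10% one-year mortality, every patient staying 14 days on the ward (COVID-19) or 7 days (comparator), clock at ICU discharge, no adjustment for ward stay. The ratio of time at risk, (t − 14)/(t − 7), gives 16/23 = 0.70 at 30 days, 46/53 = 0.87 at 60 and 351/358 = 0.98 at 365. The large-sample Cox limit, found by numerical integration, is 0.695, 0.867 and 0.979. With the stays reversed it is 1.44, 1.15 and 1.02. Equal stays give 1.00.

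**4. Does adjusting for ward stay help or harm?** Simulated with 300,000 per group, 15% one-year risk and variable ward stays averaging 14 or 20 versus 10 days, under a flat or falling hazard. Unadjusted 30-day ratios were 0.65 to 0.88. With ward stay in the model, ratios were 0.97 to 1.02 at all horizons examined (30 to 365 days). Adjustment largely absorbs the distortion.

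**5. Which clock?** Set-up of step 3, but with a hazard that falls after hospital discharge (Weibull shape 0.7), true ratio 1:

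| Analysis | 30 days | 365 days |
|---|---|---|
| ICU-discharge clock, no correction, fixed stays | 0.774 | 0.985 |
| ICU-discharge clock, no correction, exponential stays | 0.790 | 0.985 |
| Delayed entry at hospital discharge, fixed stays | 1.373 | 1.055 |
| Delayed entry at hospital discharge, exponential stays | 1.072 | 1.033 |
| Clock at hospital discharge | 1.00 | 1.00 |

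Delayed entry returns 1.00 under a flat hazard, but under a falling one it leaves a larger one-year error than doing nothing.

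**6. Selection.** From SAP 2.2, hospital survival is 5,000/10,000 = 50% with COVID-19 and 100,000/130,000 = 77% for emergency ICU admissions before the pandemic.

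**The case against.** The strongest reply is that the target population is hospital survivors and the stated origin is ICU discharge. ICU stay, ventilation and organ support are complete by then, and Protocol 11.2 also lists days of ventilation for the propensity score. Comparing patients with the same ICU course is therefore legitimate. This stands. A reader might infer that adjusting for variables arising after admission invalidates the matched hazard ratios; the documents do not support that. What is missing is a statement of the target and a counterpart that shows the difference.

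An admission-only model does not fully answer section 6 either, because it still conditions on hospital survival. This also stands, and is a reason to say so in the report.

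On ward time, the post-ICU stay is already on the 5.2 list, and adjusting for it repairs the distortion rather than causing it. A reader might infer that the one-year primary result is materially biased; in the flat-hazard example the effect there is about 2%, even unadjusted. The point also depends on time zero. If the hospital-discharge wording governs, ward time precedes follow-up and the problem disappears.

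It might also seem that delayed entry should be imposed throughout. Step 5 shows why not: at one year it can do worse than no correction.

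**Conclusion.** The point holds as a cheap improvement. The text establishes that the adjusted analyses in SAP section 5 are conditional on ICU course, that this target is not stated, and that no specified adjusted analysis uses admission variables alone. SAP 5.1 is wrong to describe the four lengths as characteristics at ICU admission.

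The numerical consequence is not established. The factor of about 0.94 to 1.18 rests on assumed ventilation hazard ratios, a yes/no simplification and ventilation shares for admissions. The actual difference could be larger, nil or of either sign.

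The ward-time distortion is real only if follow-up starts at ICU discharge and ward stays differ. It then falls mainly on unadjusted results at 30 to 90 days. Ward stays and the shape of the hazard are assumptions; the documents give neither.

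**What to change.** 1. For death, in each main cohort comparison, add one adjusted analysis using the 5.2 list without the four lengths, with its clock at hospital discharge. The two changes belong together: dropping ward stay while keeping the ICU-discharge clock would bring in the ward-time distortion. Report it beside the full-list analysis, label the two *given admission case mix* and *also given ICU course*, and state before analysis which is primary. That choice is the sponsor's.
2. Reconcile time zero between the ICU-discharge and hospital-discharge wordings. If ICU discharge is kept, repeat the unadjusted and matched death analyses with the clock at hospital discharge, at least at 30 to 180 days. Do not impose delayed entry in all models.
3. Correct SAP 5.1 so that the four lengths are not described as known at ICU admission.
4. State that all results are conditional on hospital survival, about 50% versus 77% on the SAP's counts.

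**Cost.** Item 1 adds one adjusted analysis for each of the three SAP comparator cohorts (4.4.2 to 4.4.4), or four analyses if the protocol's pneumonia comparator (11.4) is included, each with its own balance check where matching is used. The admission-only model leaves unbalanced any severity that the admission score misses. A hospital-discharge clock needs data beyond the 1 July 2021 limit in SAP 2.3, or censoring of late patients; Protocol 12.1 already requests one year after hospital discharge. Items 3 and 4, and the wording part of item 2, are text changes.

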5.3. Outcome definitions

5.3.1. Primary outcome

Death – death from any cause, as recorded in the civil registrations data set. As per Section 2.4 the primary analysis will be at one-year post-discharge. Comparisons at 30, 60, 90 and 180 days will be secondary analyses of the primary outcome.

5.3.2. Secondary outcomes

Cause-specific readmissions will be identified by combining HES (ICD-10) and GDPPR coding, using coding sets defined in Ayoubkhani et al. (15). For a venous thrombotic event, we will include the following ICD-10 codes: I80.0-I80.3, I80.8-I80.9, I82.9, O22.2-O22.3, O87.0-O87.1, I26.0, and I26.9.

• Emergency hospital admission – any non-elective hospital admission. Recorded in the hospital episode statistics data set.

- Emergency hospital admission for respiratory infection any emergency hospital admission for a respiratory infection.
- Emergency hospital admission for a major adverse cardiac event (myocardial infarction, stroke, acute heart failure)
- Emergency hospital admission for a venous thrombotic event (deep vein thrombosis or pulmonary embolism)
- Development of end stage renal failure treated by renal replacement therapy

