11.2. Description of the Statistical Methods

Primary outcome

The primary outcome will be all-cause mortality at 1 year after discharge from ICU. For patients transferred between ICUs, this will be the time of discharge from the last ICU. Dates of death will be extracted from Civil Registration (deaths).

Secondary outcomes

Secondary outcomes will be:

- All-cause mortality at 30, 60, 90 and 180 days
- Any emergency (non-elective) hospital admission
- Emergency hospital admissions for respiratory infection
- Emergency hospital admission for a venous thrombotic event (deep vein thrombosis or pulmonary embolism)
- Emergency hospital admission for a major adverse cardiac event (myocardial infarction, stroke, heart failure)
- Development of end stage renal failure treated by renal replacement therapy

Reasons for hospital admission (i.e. primary diagnosis) will be identified using the International Classification of Diseases 10th Edition (ICD- 10) codes obtained by linkage to the HES/PEDW. Where required, ICD-10 codes will be assigned to broader diagnostic groups (e.g. respiratory infections) as per the UK Summary Hospital-level Mortality Indicator (SHMI) (16).

Statistical methods

For patients treated on ICU for COVID-19 and comparator groups, we will report the unadjusted proportions/incidence of primary and secondary outcomes, along with cumulative incidence function estimates over the 1 year follow-up period. When considering secondary outcomes (and where appropriate), the cumulative incidence estimates will account for the competing risk of death. For the COVID-19 group, we will also investigate the effect of ICU admission time (i.e. early epidemic, late epidemic) as this may impact their outcomes, as treatments changed over time.

We will compare the risk of the primary and secondary outcomes between the COVID-19 and comparator groups using survival models, such as Cox proportional hazards regression models or Fine and Gray models (when death is a competing risk). We will fit both univariable models (i.e. just including the COVID-19 vs comparator group variable) and multivariable models including potential confounders.

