11.4. Analysis populations

Primary group

Our primary group will be patients admitted with confirmed COVID-19 between 1st January to 1st July 2020.

Comparator groups

The primary comparator group will be patients admitted to ICU with viral or bacterial pneumonia between 1st July 2016 and 1st July 2019.

Secondary comparator groups will include:

- All emergency ICU admissions between 1st July 2016 and 1st July 2019
- All emergency ICU admissions between 1st July 2016 and 1st January 2020 where the primary diagnosis was not COVID-19
- All emergency ICU admissions between 1st January and 1st July 2020 where the primary diagnosis was not COVID-19

Pregnant patients

We will undertake a sub-group analysis in patients who were pregnant when treated for COVID-19 on ICU between 1st January and 1st July 2020.

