2.2. Sample size, power, and detectable difference

The study size will be determined by the number of ICU survivors available from the CMP. The CMP currently holds around 10,000 patients admitted with confirmed COVID-19 between January and July 2020, of which ≈5,000 survived to hospital discharge. Of the survivors, we expected 90% (4,600) to have been admitted to an ICU in England or Wales.

Prior to the COVID-19 pandemic, there were around 130,000 emergency ICU admissions per annum in the CMP. Of these, around 100,000 survived to hospital discharge. We expect ≈90,000 to have been admitted to an ICU in England or Wales.

Study participants will include around 3.5 years of pre-pandemic admissions (90,000 x 3.5 = 315,000) and 4,600 COVID admission during the pandemic giving a total sample size of 319,600.

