3.1. Multiplicity

We do not plan to make any adjustments to p-values or confidence intervals. To reduce the impact of multiple testing, we will only report p-values for the primary outcome measure (i.e. death). All analyses of secondary outcomes will only present the effect size and the 95% confidence interval.

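### The ICD-10 list for the venous thrombotic outcome is broader than deep vein thrombosis or pulmonary embolism and has no obstetric embolism code

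*SAP*

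**What the plan says.** Both documents give the same clinical definition. SAP 5.3.2 words the outcome as "Emergency hospital admission for a venous thrombotic event (deep vein thrombosis or pulmonary embolism", and the objectives tables (Protocol 6, SAP 1.2) and Protocol 11.2 also limit it to those two conditions.

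For this outcome the SAP supplies its own codes: "we will include the following ICD-10 codes: I80.0-I80.3, I80.8-I80.9, I82.9, O22.2-O22.3, O87.0-O87.1, I26.0, and I26.9". It gives no reason for the choice and does not mention superficial events.

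Two other statements bear on how events are found. SAP 5.3.2 says "Cause-specific readmissions will be identified by combining HES (ICD-10) and GDPPR coding", using code sets from a cited study that are not reproduced. Protocol 11.2 takes the reason for admission to be the primary diagnosis, identified from "International Classification of Diseases 10th Edition (ICD- 10) codes obtained by linkage to the HES/PEDW".

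On pregnancy, Protocol 11.4 says "We will undertake a sub-group analysis in patients who were pregnant when treated for COVID-19 on ICU", and both objectives tables list a comparison of pregnant patients with age-matched controls as exploratory. On reporting, SAP 3.1 says "All analyses of secondary outcomes will only present the effect size and the 95% confidence interval".

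**The concern.** A code list is the working definition of an outcome in linked routine data: an admission counts if its code is listed. Here the list and the clinical wording differ in two ways.

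- **Too broad.** Three listed codes appear to be superficial thrombophlebitis, which is neither DVT nor PE. An emergency admission for one of these would count the same as an admission for PE.
- **A gap.** The list covers vein events in pregnancy and the puerperium (O22, O87) but has no O88 code, so obstetric blood-clot embolism is not among the listed events.

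The secondary objective is to estimate risk as well as to compare it, and SAP 5.4.1 commits to tabulated counts, proportions and cumulative incidence curves for each cohort. Superficial events enter those absolute figures even when they are equally common in every cohort. They also enter the cause-specific hazard ratio of SAP 5.4.2. Because secondary outcomes are reported without p-values, the estimate and its interval are the whole result. Venous thrombotic complications are among those that the background sections cite for COVID-19.

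**Working it through.** **No planned figure to reproduce.** No sample size, power or event count in either document depends on this list. SAP 2.2 says "The study size will be determined by the number of ICU survivors available from the CMP". Neither document gives a rate for this outcome, the share of events under superficial codes, or the number of pregnant patients.

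**Step 1: set the list against the definition.** The titles below are the standard ICD-10 ones. The documents name the classification but do not print titles, so this step is an assumption to verify.

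| Codes | Meaning under standard titles | In the list? | Fits DVT or PE? |
|---|---|---|---|
| I80.1, I80.2, O22.3, O87.1 | deep vein events, including obstetric | yes | yes |
| I26.0, I26.9 | pulmonary embolism | yes | yes |
| I80.3, I80.8, I80.9, I82.9 | unspecified or other site or vessel | yes | cannot be told from the code |
| I80.0, O22.2, O87.0 | superficial thrombophlebitis | yes | no |
| O88.2 | obstetric blood-clot embolism | no | the obstetric embolism code |

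So the list measures DVT and PE, plus some superficial and unspecified events, less any obstetric embolism recorded only under O88.2.

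**Step 2: effect of superficial codes on the hazard ratio.** Let f be the share of counted comparator events that are superficial, and HR_sup the hazard ratio for superficial events. Hazards add, so

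HR_obs = (1 − f) × HR_true + f × HR_sup.

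Take HR_sup = 1.0 (superficial events unrelated to cohort) and f from 5% to 30%. All of these values are assumed.

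- HR_true = 2.0: f = 5% gives 0.95 × 2.0 + 0.05 = 1.95; f = 30% gives 0.70 × 2.0 + 0.30 = 1.70.
- HR_true = 1.5: f = 5% gives 0.95 × 1.5 + 0.05 = 1.475; f = 30% gives 0.70 × 1.5 + 0.30 = 1.35.

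The pull towards 1 depends on HR_sup = 1.0. If HR_sup equals HR_true the ratio is unchanged, and if HR_sup is larger the observed ratio overstates the DVT or PE effect.

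**Step 3: effect on incidence.** With no missed events, counted comparator incidence is 1 / (1 − f) times the DVT and PE incidence: 1 / 0.95 = 1.05 at f = 5% and 1 / 0.70 = 1.43 at f = 30%.

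**Step 4: the obstetric gap.** If a fraction m of true events is missed equally in both cohorts, the ratio for those events is unchanged and their incidence is multiplied by (1 − m). In the full cohorts m can come only from pregnant or recently delivered patients. Among pregnant patients themselves it could be much larger, but nothing in the documents allows it to be estimated.

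**The case against.** The strongest reply is that the case depends on titles the documents do not print. That stands as a caveat but does not remove the point. The SAP states the outcome in bare ICD-10 codes, which cannot be applied without the classification, and the titles are quick to check. Claims about how hospitals code in practice are different, and the point does not rely on them.

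Three stronger readings are tempting, and the documents support none of them.

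- *The list fails to measure DVT or PE.* It does not fail: the main codes for both are present.
- *PE in a pregnant patient can never count.* This is not shown. Primary-care coding and the cited code sets also feed cause-specific readmissions, and their content is not visible. They might fill the gap. They would not remove superficial codes that are already listed.
- *Phlebitis from cannulas or lines will swamp the outcome, for example through I80.8.* The outcome is an emergency admission, and Protocol 11.2 takes the reason for admission to be the primary diagnosis. Phlebitis during the index stay would not count. Only an event serious enough to be the main reason for a new emergency admission would.

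It can also be said that a broad definition was intended. If so, the outcome's label is wrong in both documents, and label and codes still need to be reconciled.

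Finally, the reach is limited. This is one of several secondary outcomes, and the pregnancy comparison is exploratory, of unstated size and not among the subgroups in SAP 5.5. That stands, and it bounds the importance of the point.

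**Conclusion.** The list and the stated outcome do not match. On standard ICD-10 titles, three codes bring in superficial thrombophlebitis, and obstetric embolism is not listed. Followed as written, the list would put non-outcome events into the reported incidence and hazard ratios.

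The size cannot be computed from the documents. On the assumed shares the distortion runs from almost nothing (2.0 seen as 1.95) to moderate (2.0 seen as 1.70), and the low end is as compatible with the plan as the high end. The direction towards 1 holds only if superficial admissions are unrelated to cohort. The obstetric gap has little bearing on the main comparison and matters chiefly for the exploratory analysis of pregnant patients. The primary outcome, death, is unaffected. This is a modest correction, worth making because it is cheap and fixes the definition in advance of results.

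**What to change.** In SAP 5.3.2 do one of the following.

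1. **Align the list with the definition (preferred).** Remove I80.0, O22.2 and O87.0 and add O88.2. The list becomes I80.1-I80.3, I80.8-I80.9, I82.9, O22.3, O87.1, O88.2, I26.0 and I26.9.
2. **Align the definition with the list.** Keep the broad list, relabel the outcome so that it says superficial events are included, and add an analysis restricted to the DVT and PE codes.

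Under either option, check each title against the classification, and state whether the primary-care coding and the cited code sets also define this outcome and whether they cover obstetric embolism.

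Leave I80.3, I80.8, I80.9 and I82.9 in the main outcome. Removing them would trade true events for specificity, so at most test their exclusion in a sensitivity analysis.

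The cost is a short edit to the SAP text and the code list, with no new data. The downside of option 1 is slightly fewer counted events. If outcome data have already been analysed, report the change as a deviation under SAP 3.3.
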